### **5.0 Eligibility and Exclusion Criteria**

**Inclusion criteria:**

1. Patient undergoing total knee arthroplasty with regional anesthesia planned for postoperative analgesia.
2. Adult, 19 years of age or older
3. Patient classified as American Society of Anesthesiology (ASA) class I, II, or III

**Exclusion criteria:**

1. Any subject not classified as an ASA I, II, or III
2. Allergy/intolerance to local anesthetic
3. Pre-existing neurologic or anatomic deficit in lower extremity on the side of the surgical site
4. Coexisting coagulopathy such as hemophilia or von Willebrand disease.

## **6.0 Randomization and Recruitment Procedures**

Recruitment: Participants will be recruited, identified, and interviewed by either the study Principal Investigator or one of the co-investigators. The interviewing investigator will confirm eligibility and the absence of any exclusionary criteria. Details of the study (including risks) will be explained to prospective participants to their satisfaction and consent forms will then be signed.

Randomization: Upon enrollment into the study, participants will be randomized 1:1 to either the investigational group (*adductor canal nerve catheter*) or the control group (*femoral nerve catheter*). Randomization will be performed using a random number generator.

## **7.0 Study Interventions and Procedures**

- A. Investigational group participants in the adductor canal block arm will receive an adductor canal block catheter placed under direct ultrasound guidance as follows.
  - a. Patients will be placed supine with their block limb supinated about 20 degrees to facilitate access to the anteromedial thigh. Standard noninvasive monitors will be applied, and oxygen administered via nasal canula. Parenteral midazolam and fentanyl will be titrated to patient comfort.
  - b. Standard skin sterilization, prepping, and draping will be applied to the area. Under ultrasound guidance the needle will be advanced into the adductor canal. After negative aspiration, a bolus of 20 ml 0.5% Ropivacaine will be injected under direct visualization in 5 mL aliquots ensuring proper placement of the needle tip. The catheter will be advanced in this position at least 2 cm and not more than 5 cm and secured to the skin with tegaderm.
  - c. Patients will be evaluated immediately post-operatively in the PACU to determine VAS score from 0-10.

- d. Patients will be given a standard pain regimen while in the hospital. 24 hour opioid consumption will be calculated.
- e. Patients will be evaluated 24 and 48 hours post operatively for VAS score, duration of sensory and motor block, and patient satisfaction from 0-10. The catheter will be removed on post operative day 2.
- f. Patient will be followed up until nerve block resolved.
- g. Physical therapists in the hospital will be surveyed with a standard questionnaire regarding the patients ability to participate in physical therapy sessions on a scale of 0-10. Ambulation distance at 24 and 48 hours will be recorded per their notes.
- h. The surgeons performing the procedures will be surveyed in a general sense regarding their impression of patient recovery with this block
- i. Calculate the hours to discharge for each patient.

B. Control group participants in the femoral nerve block arm will receive a femoral nerve block catheter placed under direct ultrasound guidance with the stimulating needle as follows.

- a. Patients will be placed supine with their block limb exposed to facilitate access to the anterior inguinal area. Standard noninvasive monitors will be applied, and oxygen administered via nasal canula. Parenteral midazolam and fentanyl will be titrated to patient comfort.
- b. Standard skin sterilization, prepping, and draping will be applied to the area. Under ultrasound guidance the needle will be advanced to the femoral nerve. After negative aspiration, a bolus of 20 ml 0.5% Ropivacaine will be injected under direct visualization in 5 mL aliquots ensuring proper placement of the needle tip. The catheter will be advanced in this position at least 2 cm and not more than 5 cm and secured to the skin with tegaderm.
- c. Patients will be evaluated immediately post-operatively in the PACU to determine VAS score from 0-10.
- d. Patients will be given a standard pain regimen while in the hospital. 24 hour opioid consumption will be calculated.
- e. Patients will be evaluated 24 and 48 hours post operatively for VAS score, duration of sensory and motor block, and patient satisfaction from 0-10. The catheter will be removed on post operative day 2.
- f. Patient will be followed up until nerve block resolved.
- g. Physical therapists in the hospital will be surveyed with a standard questionnaire regarding the patients ability to participate in physical therapy sessions on a scale of 0-100. Ambulation distance at 24 and 48 hours will be recorded per their notes.
- h. The surgeons performing the procedures will be surveyed in a general sense regarding their impression of patient recovery with this block
- i. Calculate the hours to discharge for each patient.

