### **4.0 Objectives and Hypothesis**

Following are the specific objectives of this study:

1. Determine the effectiveness of ACB for analgesia compared to FNB as determined by patient reported VAS scores
2. Determine the effectiveness of ACB for analgesia compared to FNB as determined by opioid usage
3. Determine the effectiveness of ACB in physical therapy as determined by early ambulation distance
4. Determine surgeon satisfaction via survey.
5. Determine if there is any difference in time to discharge between the two blocks.

Outline of therapy: Participants in the investigational group will receive an adductor canal nerve catheter prior to TKA surgery. Participants in the control group will receive a femoral nerve catheter prior to TKA surgery. After surgery, the patient will be seen in the recovery room to bolus the catheters and start continuous infusions of ropivacaine. Further details are below in section #

Following are primary endpoints:

1. Pain scores (VAS) at immediate post op, 24 hours, and 48 hours, including highest
2. Opioid consumption at 24 hours and 48 hours pain score at any given time post operatively.
3. Physical therapist assessment of patient participation 0-100.
4. Distance ambulated at 24 hours and 48 hours
5. Patient satisfaction
6. Surgeon satisfaction
7. Hours to discharge.

Study Hypothesis: We hypothesize that the ACB will become the standard of care for TKA analgesia on the basis of improved physical therapy participation and increased patient satisfaction without sacrificing analgesia. With better physical therapy participation, there would be quicker recovery and potentially earlier discharge, increasing patient and surgeon satisfaction.

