## 8.0 Statistical Considerations

**General Data Analysis:** All demographic and clinical variables with continuous measures will be expressed as means and standard deviations; categorical factors will be expressed as proportions. For non-normal data, the medians and inter quartile ranges will be displayed. The distribution of the continuous factors will be examined using the Kolmogorov-Smirnov test. For data that are normally distributed, the one-way ANOVA and Student's t-test will be used to compare groups of data. For data that are not normally distributed, the Kruskal-Wallis and Mann-Whitney tests will be used for comparisons. Chi-square and Fisher's exact tests will be used to analyze categorical data. For all comparisons, a value of  $p < 0.05$  will be considered statistically significant.

**Primary Outcome Analysis:** Statistical analyses will be performed using SAS for Windows, version 9.2. Student's t-test will be used to compare post-operative pain scores for investigational and control subjects. Linear regression will be also be used to test the relationship between pain scores and regional anesthetic technique, while controlling for relevant clinical and demographic variables. Distance of first ambulation will be analyzed using Cox proportional hazards model. Student's t-test will be used to compare patient and surgeon satisfaction.

**Statistical Power and Sample Size Estimates:** Sample size (100) was determined using a Cohen's d table assuming a mean pain VAS score of 8 ( $sd = 3$ ) on a scale of 0-10 for control subjects. A sample of 100 participants (50 patients per treatment group) will have approximately 80% power to detect a reduction in pain score of at least 50%, and approximately 99% to detect an 80% reduction in pain score.

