## 9.0 Patient Safety and Data Security Monitoring

**Assessment of Level of Risk:** Minimal risk. Participants in this study have the risk associated with peripheral nerve block including pain and discomfort from the procedure, excessive bleeding, infection, nerve damage and failed analgesia. Both blocks are currently performed in this institution for this indication. The study would simply compare the two existing procedures to each other.

**Oversight of this investigation will be provided by:** Oversight for this clinical study will be provided by principal investigator (PI), [name], Ph.D., who is an Assistant

Professor of Anesthesiology at the University of Alabama at Birmingham (UAB). The study primary co-investigator, [name]., is an anesthesiology resident at the University of Alabama at Birmingham (UAB).

Mechanisms for HIPAA compliance: The de-identified study data will first be entered onto standardized, preprinted data collection sheets that will have no patient identifiers on them such as name, medical record number and date of surgery.

The study data will be collected and stored on a secure research server maintained by the Department of Anesthesiology. The research server is HIPAA compliant, has researcher specific restricted access, and is password protected. This research server is backed up to another secure research server at a different location. The list of patients participating in the study with their medical record numbers and dates of surgery will be kept separately and securely in a locked filing cabinet in the locked office of [name] and will be destroyed, after final data analysis, using the UAB contracted confidential shredding service. The original paper data collection forms will be disposed of using the UAB contracted confidential shredding service after the de-identified data have been transferred to the password-protected, computer database. From that point in time onward, all study participants will be identified only by their individual study specific number, both on the above server and the backup server.

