### **Appendix C: Physical Therapist Survey**

How far was the patient able to walk in his/her first ambulation trial?

On a scale of 1 to 10 (1 being worst, 10 being best), how well was the patient able to participate in physical therapy sessions while in the hospital? \_\_\_\_\_

Do you think the patient was limited primarily by pain or weakness?

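### Therapist-rated participation, a listed primary endpoint, is given as 0-100, 0-10 and 1-10 in different places, with the two arms' procedure steps disagreeing

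*Combined protocol and SAP*

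**What the plan says.** The range of the therapist's participation rating is stated in four places:

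| Place | Applies to | Range |
|---|---|---|
| Section 4.0, primary endpoint 3 | both arms | 0-100 |
| Section 7.0, step A.g | adductor canal arm | 0-10 |
| Section 7.0, step B.g | femoral arm | 0-100 |
| Appendix C, therapist form | no arm named | 1-10 |

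- Endpoint 3 reads "Physical therapist assessment of patient participation 0-100".
- Step A.g has "ability to participate in physical therapy sessions on a scale of 0-10".
- Step B.g, otherwise identical to A.g, has "ability to participate in physical therapy sessions on a scale of 0-100".
- The Appendix C item reads "On a scale of 1 to 10 (1 being worst, 10 being best), how well was the patient able to participate in physical therapy".

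Two statements point towards one common instrument. Both A.g and B.g say "Physical therapists in the hospital will be surveyed with a standard questionnaire", and section 9.0 says "study data will first be entered onto standardized, preprinted data collection sheets". Neither A.g nor B.g names Appendix C. Section 8.0 names no test specifically for this endpoint and gives no range, conversion or order of precedence. The endpoint therefore falls under the general rule there: Student's t-test for normally distributed data, and otherwise "the Kruskal-Wallis and Mann-Whitney tests will be used for comparisons".

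**The concern.** The hypothesis in section 4.0 prefers the adductor canal block "on the basis of improved physical therapy participation and increased patient satisfaction". Participation is thus one of the two grounds on which the new block is expected to be better, and section 2.0 lists its assessment among the things this study adds to earlier work.

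The only difference in wording between A.g and B.g falls exactly along the randomised comparison. If site staff follow the two steps as written, the arms are scored on scales that differ tenfold, and a raw comparison measures the scale and not the block. If everyone uses the Appendix C form, the arms are comparable, but the endpoint definition and both procedure steps then misdescribe what was recorded. In either case the choice of range is left open until scores have been collected.

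**Working it through.** **How many statements must change.** If 0-100 is intended, A.g and Appendix C are wrong. If 0-10 is intended, endpoint 3, B.g and Appendix C are wrong. If 1-10 is intended, endpoint 3, A.g and B.g are wrong. So at least two of the four must change. Aligning A.g with B.g alone is not enough, because neither of their ranges matches the form.

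**What one number means on each range.** Position = (score − minimum)/(maximum − minimum). For a score of 8:

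- 0-100: 8/100 = 8%
- 0-10: 8/10 = 80%
- 1-10: (8 − 1)/(10 − 1) = 7/9 = 77.8%

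Conversely, a patient 70% of the way up the range scores 70, 7.0 and 1 + 9 × 0.7 = 7.3 respectively. A score of 0 is allowed by endpoint 3 but cannot be entered on the form.

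**Effect on the comparison when there is no true difference.** The documents give 50 patients per arm and p < 0.05. They give no mean or SD for this endpoint, so I assume means of 3 to 9 and SDs of 1 to 3 on a ten-point range, and two-sided tests.

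For the literal reading with raw scores, a hand calculation is enough. With mean m and SD s on 0-10, the other arm has mean 10m and SD 10s. Ignoring truncation at the ends of the scale:

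- difference in means = 10m − m = 9m
- standard error = √((s² + 100s²)/50) = s√2.02 = 1.42s
- assumed case with the smallest ratio, m = 3 and s = 3: 27/4.26 = 6.3 standard errors
- middle case, m = 7 and s = 2: 63/2.84 = 22 standard errors

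Simulation covered 12 settings (means 3, 5, 7, 9 by SDs 1, 2, 3), with 4,000 trials each and the same normal latent score in both arms. Scores on 0-10 were rounded to whole numbers. Scores on 0-100 were ten times the latent score, in steps of 1, 5 or 10 (1 or 5 in the last row of the table). The 1-10 form was filled in either by linear mapping or by rounding with a floor of 1. False-positive rates, as minimum to maximum over settings and rounding rules:

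| How scores are recorded | t-test | Mann-Whitney |
|---|---|---|
| A.g and B.g literal, raw scores | 100% | at least 99.9% |
| A.g and B.g literal, 0-100 divided by 10 | 4.1%-5.6% | 4.3%-6.5% |
| Appendix C form in both arms | 4.3%-5.8% | 4.5%-5.5% |
| 0-100 in both arms | 4.5%-5.5% | 4.2%-5.4% |

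In the first row the femoral mean is 9.98 to 10.06 times the adductor canal mean. The simulation standard error near 5% is √(0.05 × 0.95/4,000), about 0.3 percentage points.

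**The case against.** The strongest reply is that this is an editorial slip without consequence for the comparison. Both arms' steps refer to a standard questionnaire. The only therapist form in the available text asks about the same thing in nearly the same terms, and it names no arm. One common form is the natural reading, and then the arms are comparable. Only the raw, unrescaled literal reading damages inference. It would probably be noticed at data entry, and the 100% figure does little more than restate that one arm was multiplied by ten. The endpoint also carries less weight than its label suggests: all seven items are called primary, the sample size rests on pain alone, and the primary analysis paragraph in section 8.0 does not mention therapist participation. Finally, some pages and the data collection sheets are not in the available text, so a governing rule could exist there.

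Most of this stands as a limit on weight. The documents do not establish that the arms will be scored differently, and a mean reported with its form and anchors can be interpreted. But the common-form reading does not remove the contradiction. It makes three of the four statements wrong, including the endpoint definition. Nor is 0-100 a single slip, since it appears twice.

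**Conclusion.** The concern holds. A listed primary endpoint is defined on three incompatible ranges, and the available text does not say which applies. That conclusion rests on the wording alone and needs no assumption.

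The practical size depends on conduct. Under the literal reading with raw scores, a significant result is virtually certain with no true difference. With any single range, or after correct rescaling, the error rate stays near 5%. Those rates rest on the assumed means, SDs and rounding rules. Because one common form is the likelier practice, the main harm is that the reported measure would not match its own protocol definition. This should be fixed before data collection; it does not invalidate the design.

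**What to change.** Use one range with the same anchors in endpoint 3, A.g, B.g and Appendix C, and name the Appendix C form in A.g and B.g.

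The simplest version leaves Appendix C unchanged and rewords endpoint 3, A.g and B.g to 1-10 (1 worst, 10 best), recorded on the Appendix C form. That is a wording change in three places. It also keeps the therapist item on the same range as the participation questions put to patients in Appendix B and to surgeons in Appendix D.

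The alternative is 0-100 (0 worst, 100 best) throughout. This changes A.g and the Appendix C item, adds anchors to endpoint 3, and names the form in A.g and B.g. It works as a definition, but it separates the therapist item from its counterparts in Appendices B and D.

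Neither version changes visits, staffing, sample size or analysis, and section 8.0 needs no edit for this point.

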## Projected Overall Study Timeline

Aug 2014	Sep 2014	Oct 2014	Nov 2014	Dec 2014	Jan 2015	Feb 2015	Mar 2015
Startup							
	Enrollment						
				Data Entry and Analysis			
						Study Write Up	

## 8.0 Statistical Considerations

**General Data Analysis:** All demographic and clinical variables with continuous measures will be expressed as means and standard deviations; categorical factors will be expressed as proportions. For non-normal data, the medians and inter quartile ranges will be displayed. The distribution of the continuous factors will be examined using the Kolmogorov-Smirnov test. For data that are normally distributed, the one-way ANOVA and Student's t-test will be used to compare groups of data. For data that are not normally distributed, the Kruskal-Wallis and Mann-Whitney tests will be used for comparisons. Chi-square and Fisher's exact tests will be used to analyze categorical data. For all comparisons, a value of  $p < 0.05$  will be considered statistically significant.

**Primary Outcome Analysis:** Statistical analyses will be performed using SAS for Windows, version 9.2. Student's t-test will be used to compare post-operative pain scores for investigational and control subjects. Linear regression will be also be used to test the relationship between pain scores and regional anesthetic technique, while controlling for relevant clinical and demographic variables. Distance of first ambulation will be analyzed using Cox proportional hazards model. Student's t-test will be used to compare patient and surgeon satisfaction.

**Statistical Power and Sample Size Estimates:** Sample size (100) was determined using a Cohen's d table assuming a mean pain VAS score of 8 ( $sd = 3$ ) on a scale of 0-10 for control subjects. A sample of 100 participants (50 patients per treatment group) will have approximately 80% power to detect a reduction in pain score of at least 50%, and approximately 99% to detect an 80% reduction in pain score.

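### Covariate adjustment is planned only for the additional pain regression; extending it, with age and ASA class named, could make the other endpoints more precise at no cost in patients

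*Combined protocol and SAP*

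**What the plan says.** Section 8.0 sets a general default for continuous data: "For data that are normally distributed, the one-way ANOVA and Student's t-test will be used to compare groups of data". Kruskal-Wallis and Mann-Whitney take over when the data are not normal. Neither route involves covariates.

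Under Primary Outcome Analysis, pain has a t-test and a second analysis: "Linear regression will be also be used to test the relationship between pain scores and regional anesthetic technique", controlling for clinical and demographic variables that are not named. The plan does not say which of the two decides. Satisfaction has an unadjusted comparison: "Student's t-test will be used to compare patient and surgeon satisfaction". First-ambulation distance is assigned a Cox model, with no covariates listed or ruled out. Opioid consumption, therapist-rated participation, hours to discharge and distance at 24 and 48 hours have no analysis of their own, so the default applies. Section 4.0 lists all of these as primary endpoints.

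Two baseline variables are certain to be known. Section 5.0 checks age (19 or older) and ASA class: "Patient classified as American Society of Anesthesiology (ASA) class I, II, or III". Section 6.0 describes 1:1 randomization from a random number generator and mentions no stratification. Section 4.0 expects the adductor canal block to win "on the basis of improved physical therapy participation and increased patient satisfaction without sacrificing analgesia", with earlier discharge as a possible consequence.

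**The concern.** The plan accepts covariate adjustment in principle but applies it to one endpoint, and gives no reason for stopping there. That endpoint is pain, where the hypothesis only asks that nothing be lost. Participation, patient satisfaction and discharge, where a benefit is expected, get unadjusted tests only.

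The eligible population is wide in age and health status. If those two characteristics predict how soon a patient goes home or how far the patient walks, leaving them out keeps explainable variation in the error term. Confidence intervals are then wider than they need be, and a true difference is less likely to be detected with 100 patients. Leaving the pain covariates unnamed also allows them to be chosen after the data are seen.

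**Working it through.** **The plan's own power figure.** Section 8.0 states "A sample of 100 participants (50 patients per treatment group) will have approximately 80% power" for a 50% reduction, "assuming a mean pain VAS score of 8" with SD 3. That is a difference of 4, so d = 4/3 = 1.33. With 50 per group and two-sided 5%, power exceeds 99.99%, so the stated figure is not reproduced. Reading the 50% as d = 0.5 gives 69.7% two-sided and 79.9% one-sided. This is a separate matter. What counts here is that the figure concerns pain only: the documents give no planned effect or power for any other endpoint.

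**Inputs.**
- From Section 8.0: 50 per group; results with p < 0.05 "will be considered statistically significant". Sidedness is not stated; two-sided is assumed.
- Assumed: d = 0.565, chosen because it gives about 80% unadjusted power. A second case uses d = 0.50.
- Assumed: R², the share of within-arm outcome variance explained by age and ASA class. The documents give no value, so a range is shown.

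**Formulas** (noncentral t, linear model, normal outcome).
- Unadjusted: df = 100 − 2 = 98; noncentrality = d × √(50/2) = 5d.
- Adjusted: age takes 1 df and ASA class 2, so df = 95; noncentrality = 5d/√(1 − R²) × √(95/98). The last factor is a conservative charge for the three covariate df.

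For d = 0.565 the unadjusted noncentrality is 2.825. At R² = 0.15 the adjusted value is 2.825/√0.85 × 0.985 = 3.02.

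| R² | Power, d = 0.565 | Change, points | Power, d = 0.50 |
|---|---|---|---|
| Unadjusted | 79.9% | – | 69.7% |
| 0 | 78.6% | −1.3 | 68.3% |
| 0.05 | 80.6% | +0.7 | 70.5% |
| 0.10 | 82.7% | +2.8 | 72.9% |
| 0.15 | 84.8% | +4.9 | 75.3% |
| 0.20 | 86.8% | +6.9 | 77.8% |
| 0.25 | 88.9% | +9.0 | 80.3% |

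**Break-even.** The two noncentralities are equal when 1 − R² = 95/98, that is R² = 0.031.

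**Equivalent patients.** The unadjusted total that matches the adjusted power is about 100 × (95/98)/(1 − R²): 96.94/0.85 = 114 at R² = 0.15 and 96.94/0.75 = 129 at 0.25. That is about 14 and 29 extra patients. The simpler 100/(1 − R²) gives 118 and 133, but it leaves out the df charge used in the table.

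**The case against.** The strongest reply is that nothing in the documents shows that age or ASA class predicts these outcomes. Below R² of about 0.03 adjustment loses power, and at 0.05 the gain is under one point. The prognostic argument is easiest to make for distance and discharge. It is weaker for a therapist's rating or a patient's satisfaction score, on which the hypothesis chiefly rests. This stands, and it is why the gain is given only as a conditional range.

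A reader might infer several stronger things that the documents do not support:

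- *The unadjusted comparisons are biased, or invalid because chance imbalance goes uncorrected.* They are not. Randomization makes them unbiased, and the test already allows for chance imbalance.
- *Pain gets the better deciding analysis.* Pain is also compared by t-test, and the regression is an addition whose status is not stated.
- *All walking distance is analysed unadjusted.* Only the 24 h and 48 h distances fall to the default tests. The Cox model for first ambulation could take covariates; the plan is silent on them.
- *Every endpoint without adjustment carries the expected benefit.* Objective 2 treats opioid use as a measure of analgesia, which the hypothesis only asks to be preserved.

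The power figures also assume a linear model with normal errors and do not carry over directly to ordinal models. A log scale fails for zero opioid use or zero distance unless zeros are provided for.

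**Conclusion.** The point holds as a low-cost improvement in efficiency and pre-specification. Pain is the only endpoint with a stated adjusted analysis, although two baseline variables are available for every patient.

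With 50 per group, two-sided 5% and an effect giving 80% unadjusted power, adjustment helps once R² exceeds about 0.03. It adds about 3 points at 0.10, 5 at 0.15 and 9 at 0.25, and the downside is about 1.3 points. Both R² and the effect size are assumptions. The documents therefore support saying that power may be forgone, not that it is lost. No conclusion of the trial would be invalid if the plan stayed as it is.

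**What to change.** In Section 8.0, before outcome data are examined:

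1. For participation, patient satisfaction, hours to discharge, opioid consumption and 24 h and 48 h distance, make the deciding analysis a linear regression of the outcome on randomized arm, with age (continuous) and ASA class (I/II/III). Report the adjusted difference with its 95% confidence interval.
2. Use the same two covariates in the pain regression, and state whether it or the t-test decides. Use them also in whatever model is kept for first-ambulation distance.
3. Name one analysis scale per endpoint in advance. If a log scale is chosen, say how zeros are handled. The participation rating must first be put on a single scale: it is 0–100 in Section 4.0 and for the control arm in Section 7.0, 0–10 for the investigational arm, and 1–10 in Appendix C.
4. Keep the unadjusted t-test or Mann-Whitney as supportive.

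The cost is a few sentences and a little programming, with no new visits, measurements or patients. Age and ASA class need to be recorded as values on the data sheet. The statistical price is three degrees of freedom.

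### The adjusted pain analysis names no covariates, and the visible plan schedules no pre-operative pain score or prior opioid use to put in it

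*Combined protocol and SAP*

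**What the plan says.** Section 8.0 (Primary Outcome Analysis) compares post-operative pain between arms by t-test and adds a linear regression of pain on technique, "controlling for relevant clinical and demographic variables". It lists no covariate. The regression is described for pain scores only; none is planned for opioid consumption.

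The pain endpoint in Section 4.0 is "Pain scores (VAS) at immediate post op, 24 hours, and 48 hours, including highest". The first scheduled score in Section 7.0 is the same in both arms: "Patients will be evaluated immediately post-operatively in the PACU to determine VAS score from 0-10". That is after the block, after sedation that includes fentanyl, and after surgery. The opioid endpoint in Section 4.0 is "Opioid consumption at 24 hours and 48 hours", which is post-operative use.

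The four exclusions in Section 5.0 concern ASA class, local anaesthetic allergy or intolerance, a deficit in the operated limb, and "Coexisting coagulopathy such as hemophilia or von Willebrand disease". None concerns opioid use. Section 6.0 randomises 1:1 with a random number generator and describes no stratification.

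Section 6.0 also has an investigator interview each candidate before enrolment: "The interviewing investigator will confirm eligibility and the absence of any exclusionary criteria". The surveys in Appendices B to D ask about the catheter period, physical therapy and the hospital course, and contain no pre-operative item.

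**The concern.** A regression that controls for clinical variables is most useful when it contains baseline values related to the outcome. Pre-operative pain is a plausible one for post-operative VAS, and prior opioid use is a plausible one for post-operative opioid consumption. Neither is visibly scheduled. A PACU score cannot stand in for a baseline, because treatment has already acted on it.

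Three things are at stake:

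- **Precision.** The Section 1.0 goal is to verify analgesic equivalence. That conclusion rests on the width of the confidence interval, so avoidable variance counts directly against it.
- **Chance imbalance.** With 50 per arm and no stratification described, prior opioid users could fall unevenly. Unless the variable is recorded, the imbalance can be neither described nor adjusted for.
- **Model choice.** With no covariate named, the adjusted model can be settled after the data are seen.

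**Working it through.** **Inputs from Section 8.0.** Control mean VAS 8, SD 3, 50 patients per arm, significance at 0.05 (sidedness not stated), stated power about 80% for a 50% reduction and about 99% for an 80% reduction. I take SD 3 for both arms and a single pain time point. The correlation r between a baseline covariate and post-operative VAS is **not in the documents**; I use 0 to 0.6 as an assumed range.

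**1. The plan's own power figure.** The standard error of the difference is 3 × √(2/50) = 0.60.

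- Read literally, a 50% reduction is 8 − 4 = 4 points. Then 4/0.60 = 6.67, and two-sided power is Φ(6.67 − 1.96), which exceeds 99.99%. The stated 80% does not reproduce.
- If 50% and 80% are read as Cohen's d of 0.5 and 0.8 with a one-sided 0.05 test, power is Φ(2.5 − 1.645) = 80.4% and Φ(4.0 − 1.645) = 99.1%. Both stated figures then reproduce.
- The same effects tested two-sided give Φ(2.5 − 1.96) = 70.5% and Φ(4.0 − 1.96) = 97.9%.

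I therefore use d = 0.5, which is 0.5 × 3 = 1.5 points, tested two-sided, as the reference. The mismatch in the stated power is a separate matter; here it only fixes the starting point.

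**2. Effect of adjusting for one baseline covariate.** The residual SD is 3 × √(1 − r²), so the standard error is 0.60 × √(1 − r²). The half-width is 1.96 × SE, and power for 1.5 points is Φ(1.5/SE − 1.96).

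| Assumed r | √(1 − r²) | SE | 95% half-width (points) | Power for 1.5 points |
|---|---|---|---|---|
| 0 | 1.000 | 0.600 | 1.18 | 70.5% |
| 0.2 | 0.980 | 0.588 | 1.15 | 72.3% |
| 0.3 | 0.954 | 0.572 | 1.12 | 74.6% |
| 0.5 | 0.866 | 0.520 | 1.02 | 82.3% |
| 0.6 | 0.800 | 0.480 | 0.94 | 87.8% |

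The standard error falls by about 2% at r = 0.2, 4.6% at 0.3, 13.4% at 0.5 and 20% at 0.6. The equivalent gain in sample size is 1/(1 − r²): 1.04, 1.10, 1.33 and 1.56 times.

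**3. Chance imbalance in prior opioid use.** The share of prior users, p, is also an assumption. The SD of the difference in proportions is √(2p(1 − p)/50). At p = 0.20 this is √(0.32/50) = 0.08, so the 95% limits are ±1.96 × 0.08, or about ±16 percentage points. At p = 0.10 the limits are about ±12 points, and at p = 0.40 about ±19.

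**4. Opioid consumption.** The plan gives no mean or SD for this endpoint, so the gain from adjusting it cannot be put in figures.

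**The case against.** The strongest reply is that silence in Section 7.0 proves little. That section does not list age or sex either, yet Section 8.0 will summarise demographic and clinical variables, so it is not the full list of data collected. Section 9.0 refers to "standardized, preprinted data collection sheets" whose fields are not shown, and the pages just before Appendix B were not available for this review. Section 9.0 also keeps the list linking patients to their medical records until final analysis, so prior opioid use could be taken from the chart during the study.

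This stands, and it limits the point. A reader might infer that the two baseline values are unavailable, or that an imbalance in prior opioid users could never be corrected. The documents show neither. They show that neither value is visibly scheduled and neither is named for the model. Pre-operative VAS is the one that most needs prospective collection, since a score nobody asked for may not be in the chart.

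Other stronger readings also fail:

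- A reader might infer that these are the strongest predictors of the outcomes. Nothing in the documents ranks predictors, and the arithmetic needs only some correlation.
- A reader might infer bias. Randomisation protects the unadjusted t-test.
- A reader might take the stated 80% power as the base and claim a rise to 84-94% for r of 0.3 to 0.6. That base does not follow from the plan's own inputs, "assuming a mean pain VAS score of 8" with SD 3 and a halving of the score.
- A reader might say the planned opioid regression lacks its key covariate. No opioid regression is planned; it would be an addition.

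Finally, the plan states no equivalence margin, so no one can say whether the narrower interval would change the conclusion.

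**Conclusion.** The point holds as a modest, inexpensive improvement and does not challenge the validity of the planned comparison. The pain regression has no named covariates, and the visible text schedules neither a pre-operative pain score nor prior opioid use, although prior users may enrol.

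For r between 0.3 and 0.6 the interval half-width narrows by roughly 0.05 to 0.24 points (1.176 − 1.122 and 1.176 − 0.941), and power for 1.5 points gains roughly 4 to 17 percentage points. At r = 0.2 the gain is negligible. These sizes rest on the assumed correlation, on SD 3 in both arms, and on reading the target effect as d = 0.5 tested two-sided. That baseline values are not recorded at all is not established; that the plan does not commit to recording or using them is.

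**What to change.** 1. **Record, in Section 6.0.** At the existing interview, after consent and before randomisation, record a pre-operative VAS (0-10) and, from the chart, current daily opioid use. If the data collection sheet already holds these fields, say so.
2. **Name the pain covariate, in Section 8.0.** Replace the general reference to relevant variables with a fixed list that includes pre-operative VAS.
3. **Add an opioid model.** Specify a regression of post-operative opioid consumption on technique, adjusted for prior opioid use. This is a new analysis.
4. **Set the order of results in advance.** Make the adjusted differences with 95% confidence intervals the main result for pain and opioid consumption, with the unadjusted t-test as support.

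The cost is one question and one chart field per patient, one added regression, a line in Section 6.0 and a short edit to Section 8.0. Step 4 changes which estimate leads the report, so it should be settled before any outcome data are seen. No treatment or clinical rule is affected.
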